7.1 Informed Consent

Informed consent, as documented by a signed and dated ICF, must be obtained prior to performing any study procedures. Results (e.g., from laboratory tests or radiographic evaluations, etc.) obtained prior to the date of informed consent but within the allowed timeframe may be used for determination of patient eligibility only if obtained as part of standard care. For additional details, please refer to [Section 10.3](#).

7.2 Demographics and Baseline Characteristics

These assessments include:

- Demographic information such as age, gender, ethnicity, and race; to the extent allowed by local regulations.
- Cancer medical history, which includes a complete history of all surgeries and significant diagnoses, and all cancer treatments, including surgery, radiation therapy, chemotherapy, etc.
- Any significant medical history.
- Collection of information on prior medications used from ICF signature date or at least within 14 days prior to study drug administration, whichever is earlier.

7.3 Efficacy Assessments

Disease assessment will occur as per SoE ([Table 1](#) or [Table 2](#)).

Screening (Baseline) imaging should be performed within 4 weeks prior to C1D1.

During the treatment period, imaging will be performed 6 weeks and 12 weeks after C1D1, then every 12 weeks until 2 years from C1D1, then every 6 months. Imaging for disease assessment will continue until disease progression or initiation of other anti-cancer therapy (except for hematopoietic stem cell transplant). Week 6 and Week 12 imaging should be performed within ± 5 days of the scheduled time point; all other imaging should be performed within ± 2 weeks of the scheduled time point. Disease assessments should take place at the timepoints specified even if study drug dosing is delayed. Additional disease assessments may be obtained, if clinically indicated.

Response data from investigators may be collected for patients who receive chimeric antigen receptor T cells (CAR-T) therapy until 90 days after receiving CAR-T therapy.

Positron emission tomography-computed tomography (PET-CT) of the neck/neck/abdomen/pelvis and other areas of known disease or newly suspected disease, as well as a clinical examination for lymphoma, will be performed. If it is known that the tumor is FDG-avid, the baseline CT as part of the PET-CT does not have to be performed with contrast medium; however, if the baseline PET-CT shows that the tumor is not FDG-avid, diagnostic CT with IV contrast will need to be obtained as a baseline examination. For this reason, if it is known that the tumor is not FDG-avid on previous imaging, consideration should be given to obtaining a diagnostic quality CT with IV contrast as part of the initial PET-CT examination. Patients who have a contraindication to CT IV contrast medium should have MRI examinations performed instead. The assessment method determined to identify sites of disease at Baseline (i.e., PET-CT, CT, MRI) should be used for all subsequent assessments.

Patients whose tumor is not FDG-avid should have a bone marrow biopsy as part of their baseline staging and disease assessment if clinically appropriate.

The patient's response to treatment will be determined according to the 2014 Lugano Classification Criteria ([Appendix 2](#)) as CR, PR, stable disease (SD), or progressive disease (PD). Patients with clinical progression should have a radiographic disease assessment to confirm progression unless contraindicated. Radiographic disease assessment modality should be the same as that used to identify sites of disease at Baseline.

Images will be obtained according to imaging requirements as outlined in the imaging manual and will be submitted for a central/independent review. Central imaging review will be performed using two blinded independent reviewers with adjudication by a third blinded independent reviewer in cases of discordance. Submission instructions for the central/independent review will be provided in a separate manual.

7.4 Safety Assessments

Safety will be assessed based on the procedures in the subsection below. Adverse events/SAEs collection and reporting is described in [Section 8](#).

Unless otherwise specified, all safety assessments on dosing days will be done prior to study treatment administration. Additional safety assessments may be performed by the Investigator when clinically indicated.

7.4.1 Physical Examination

Planned time points for physical examination are provided in the SoE ([Table 1](#) or [Table 2](#)).

A complete physical examination will be performed at screening.

Limited, symptom-directed physical examinations should be performed at specified post baseline visits and as clinically indicated.

7.4.2 ECOG Performance Status

Eastern Cooperative Oncology Group performance status grades are presented in [Section 12.1](#), [Appendix 1](#) and will be captured at the planned timepoints provided in the SoE ([Table 1](#) or [Table 2](#)).

7.4.3 Height and Weight

Planned time points for height and weight are provided in the SoE ([Table 1](#) or [Table 2](#)).

7.4.4 Vital Signs

Planned time points for vital signs are provided in the SoE ([Table 1](#) or [Table 2](#)).

Vital signs include the measurements of arterial blood pressure (systolic and diastolic), heart rate, respiratory rate, and body temperature and will be performed according to the institutional standards.

For Day 1 of each cycle, vital signs are to be measured before the start of the infusion and at the end of infusion for patients on the loncastuximab tesirine arm; vital signs will be measured once during visit for patients on the idelalisib arm.

7.4.5 Laboratory Tests

Samples will be collected at the time points specified as per SoE ([Table 1](#) or [Table 2](#)).

Additional sample(s) may be collected and analyzed if clinically indicated. The C1D1 laboratory tests do not need to be repeated if the laboratory tests for eligibility were done within 3 days of C1D1.

Hematology: red blood cell (RBC), white blood cells (WBC) with 5-part differential (neutrophils, eosinophils, basophils, lymphocytes, and monocytes), platelet count, hemoglobin, and hematocrit.

Chemistry: ALT, AST, GGT, ALP, amylase, lipase, total bilirubin (conjugated and unconjugated bilirubin only when total bilirubin is abnormal), sodium, potassium, chloride, phosphorus/phosphate, calcium, magnesium, blood urea nitrogen or urea, carbon dioxide/bicarbonate, creatinine, creatinine clearance, creatine phosphokinase, total protein, albumin, glucose, and lactate dehydrogenase, uric acid.

Coagulation: partial thromboplastin time (PTT)/activated PTT (aPTT) and International Normalized Ratio (INR).

Urinalysis: pH, specific gravity, protein, WBC, RBC, ketones, glucose, and bilirubin.

Urinalysis may be performed by dipstick. Abnormal findings will be followed up with a microscopic evaluation and/or additional assessments as clinically indicated. A microscopic evaluation consists at a minimum of WBC and RBC quantitation per high power field, as well as semi-quantitative assessment of other cells and substances, if present, such as epithelial cells, bacteria, and crystals (“few,” “moderate,” “many”). Other evaluations depending on microscopic findings may be added.

Other tests:

HBV and/or HCV serology tests, and viral load test if clinically indicated.

HIV serology tests, and HIV viral load and /or CD4+ T cell count if clinically indicated.

CMV screening tests: CMV IgG test, and CMV antigen or PCR test for all patients during screening period.

CMV monitoring tests: CMV antigen or PCR test for patients with positive CMV serology or history of CMV infection who are receiving treatment with idelalisib.

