Coagulation and Urinalysis	7.4.5	X					
HBV, HCV tests	7.4.5	X					
CMV IgG, Antigen or PCR test (all patients) ⁶	7.4.5	X					
HIV tests	7.4.5	X					
Pregnancy test ⁷ , if applicable	7.4.6	X	X	X	X	X	X ⁷ at \geq 9 months post last loncastuximab tesirine dose
12-lead ECG (Triplicate)	7.4.7	X	X (Pre-dose)	X (Pre-dose), EOI- only for loncastuximab tesirine arm		X	
Pre-medication	6.4		D-1 to D2	D-1 to D2	D-1 to D2		

	Protocol Section	Screening	Treatment Period			EOT	Follow-up Period (up to 3 years from EOT) Every 12 weeks
			Cycle 1	Cycle 2	Cycle 3 & Beyond		
(1 Cycle = 3 weeks)							
Day (D)		-28 to -1	1	1	1		
Loncastuximab tesirine Administration (IV infusion)	6.2.2		X	X	X		
PK sample	7.5.1		X (Pre-dose and EOI)	X (Pre-dose and EOI)	X (C3-C6: Pre-dose and EOI; C7, then every other cycle: Pre-dose)	X	
ADA sample	7.5.2		X (Pre-dose)		X (C3, then every other cycle: Pre-dose)	X	X ⁸
Patient Reported Outcomes (EQ-5D-5L)	7.6.1		X	X	X	X	X ¹⁰ Up to 1 year from EOT

	Protocol Section	Screening	Treatment Period			EOT	Follow-up Period (up to 3 years from EOT) Every 12 weeks
			Cycle 1	Cycle 2	Cycle 3 & Beyond		
(1 Cycle = 3 weeks)							
Day (D)		-28 to -1	1	1	1		
Patient Reported Outcomes (FACT-Lym)	7.6.2		X	X	X C3-C18 only	X (only if EOT occurs prior to C19)	
PROs (GP-5 and items selected from PRO-CTCAE) (Complete at home except C1D1)	7.6.3 7.6.4		X⁹ Day 1 & Day 10	X⁹ Day 10	X⁹ C3 – C9 only Day 10		
Concomitant medications	6.9	From ICF signature date or Day -14 whichever is earlier, until at least 30 days after last dose of study treatment					
Adverse events	8	AEs from ICF signature date until at least 30 days after last dose of study treatment; SAEs from ICF signature date until at least 76 days after last dose of study treatment or initiation of new anticancer therapy, whichever is earlier; thereafter only related SAEs					
1 st new anticancer treatment							X
Survival							X

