⁶CMV tests include CMV IgG and CMV antigen or PCR test at screening visit for all patients.

⁷Serum or urine β -HCG test to be done on every visit at local lab if applicable. If the urine pregnancy test is positive, a serum β -HCG test is required for confirmation. Remote pregnancy test is acceptable when patient has no required site visit planned during follow-up period. Additional tests may be obtained, if needed.

⁸Only patients who test positive for ADAs may be asked to provide additional ADA samples every 12 weeks until the ADA titer falls to the baseline level.

⁹Patients will complete PRO-CTCAE items and GP-5 at study site on C1D1; at home on Day 10 (\pm 2 day) of each cycle for up to Cycle 9.

¹⁰In the event that patients complete follow up visit at home instead of being on site, EQ-5D-5L will be completed on Visit day (+2 days).

Table 2. Schedule of Events for Idelalisib Arm

(1 Cycle = 4 weeks)	Protocol Section	Screening	Treatment Period		EOT	Follow-up Period (up to 3 years from EOT) Every 12 weeks
			Cycle 1 to Cycle 7	Cycle 8 & Beyond		
Day (D)		-28 to -1	1	15	1	
Informed consent	7.1	X				
Randomization	4.2.2		X C1 only (D-1)			
Eligibility criteria	5	X				
Demography	7.2	X				
Medical/Cancer history	7.2	X				
Physical examination	7.4.1	X	X		X	X
ECOG performance status	7.4.2	X	X		X	X
Height	7.4.3	X				
Weight	7.4.3	X	X		X	X
Vital signs ² (BP, HR, RR, Temp)	7.4.4	X	X		X	X
Disease assessment ^{3,4}	7.3	Screening, 6 weeks and 12 weeks after C1D1, then every 12 weeks until 2 years from C1D1, then every 6 months.				
Hematology ⁵	7.4.5	X	X	X	X	X
Chemistry ⁵	7.4.5	X	X	AST/ALT/total bilirubin - C1 to C4 only	X	X
Coagulation and Urinalysis	7.4.5	X				
HBV, HCV tests	7.4.5	X				
CMV IgG, Antigen or PCR test (all patients) ⁶	7.4.5	X				
CMV Antigen or PCR test (for patients with positive CMV tests or history of CMV infection) ⁷	7.4.5		X		X	X
HIV tests	7.4.5	X				
Pregnancy test ⁸ , if applicable	7.4.6	X	X		X	X

	Protocol Section	Screening	Treatment Period		EOT	Follow-up Period (up to 3 years from EOT) Every 12 weeks
			Cycle 1 to Cycle 7	Cycle 8 & Beyond		
(1 Cycle = 4 weeks)						
Day (D)		-28 to -1	1	15	1	
12-lead ECG (Triplicate)	7.4.7	X	X C1-C2 only (Pre-dose)			X
Idelalisib Administration	6.2.2		Twice daily orally			
Patient Reported Outcomes (EQ-5D-5L)	7.6.1		X		X	X ¹⁰ Up to 1 year from EOT
Patient Reported Outcomes (FACT-Lym)	7.6.2		X		X C8-C18 only	X (only if EOT occurs prior to C19)

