Grade 4 infusion related reaction	
• Permanently discontinue loncastuximab tesirine
Hy's law (AST and/or ALT $> 3 \times \text{ULN}$ and bilirubin $> 2 \times \text{ULN}$)	
• Permanently discontinue loncastuximab tesirine. Hy's law defined as: AST and/or ALT $> 3 \times \text{ULN}$ and bilirubin $> 2 \times \text{ULN}$, and without initial findings of cholestasis (ALP activity $< 2 \times \text{ULN}$) and no other reason that could explain the combination of increased transaminases and serum total bilirubin, such as viral hepatitis A, B, or C, preexisting or acute liver disease, or another drug capable of causing the observed injury

Table 5. Criteria for Dose Delay or Dose Modification of Idelalisib

Toxicity	Idelalisib
Grade ≥ 2 symptomatic pneumonitis of any severity	Permanently discontinue idelalisib
Grade 2 increased ALT/AST/bilirubin or diarrhea	Maintain idelalisib dose. Monitor at least weekly until normal
Grade 3 increased ALT/AST/bilirubin or diarrhea	Withhold idelalisib. Monitor at least weekly until normal, then may resume idelalisib at 100 mg BID.
Grade 4 increased ALT/AST/bilirubin or diarrhea	Discontinue idelalisib permanently
Grade 3 neutropenia and/or thrombocytopenia	Maintain Idelalisib dose. Monitor ANC and/or platelet count at least weekly
Grade 4 neutropenia and/or thrombocytopenia	Withhold idelalisib. Monitor ANC and/or platelet count at least weekly. When neutropenia and thrombocytopenia are Grade 3 or less, may resume idelalisib at 100 mg BID
Grade ≥ 3 sepsis or pneumonia	Withhold idelalisib until infection has resolved.
Active CMV infection of any grade or viremia (positive PCR or antigen test)	Withhold idelalisib until the infection and viremia have resolved. If idelalisib is resumed, monitor by PCR or antigen for CMV reactivation at least monthly.
Suspected PJP infection of any grade.	Withhold idelalisib. Permanently discontinue idelalisib if PJP infection is confirmed.
Other Grade ≥ 3 non-hematologic toxicities	Withhold idelalisib until resolved, then may resume idelalisib at 100 mg BID. If the same grade ≥ 3 toxicity recurs after resuming idelalisib, permanently discontinue idelalisib
Anaphylaxis, Intestinal Perforation, Stevens-Johnson syndrome (SJS) and toxic epidermal necrolysis (TEN)	Permanently discontinue idelalisib

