8.1.2 Serious Adverse Events

A SAE is defined as any AE that:

- results in death.
- is life threatening.
- requires inpatient hospitalization or prolongation of existing hospitalization (hospitalization for elective procedures or for protocol compliance is not considered an SAE).
- results in persistent or significant disability/incapacity.
- is a congenital anomaly/birth defect.
- an important medical event that does not meet the preceding criteria but based on appropriate medical judgment may jeopardize the patient or may require medical or surgical intervention to prevent any of the outcomes listed above.

8.1.3 Clinical Laboratory Abnormalities and Other Abnormal Assessments as Adverse Events or Serious Adverse Events

Laboratory abnormalities (e.g., clinical chemistry, hematology, and urinalysis) or other abnormal assessments (e.g., electrocardiogram, x-rays, vital signs) without clinical significance are not recorded as AEs or SAEs. However, laboratory abnormalities/other abnormal assessments that require medical or surgical intervention or lead to pharmaceutical product interruption, modification, or discontinuation must be recorded as an AE, as well as an SAE, if applicable. If the laboratory abnormality/other abnormal assessment is consistent with a clinical diagnosis, report the adverse event using the diagnosis (i.e., anemia), not the laboratory result (i.e., decreased hemoglobin).

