9.8.1 Adverse Events

The focus of AE summarization will be on TEAEs. A TEAE is defined as an AE that occurs or worsens in the period extending from the first dose of study treatment until 30 days after the last dose of study treatment or start of new anti-cancer therapy, whichever is earlier.

All TEAEs will be summarized. Summary tables will be presented to show the number of patients reporting TEAEs by severity grade and corresponding percentages. A patient who reports multiple TEAEs within the same Preferred Term (or System Organ Class) is counted only once for that Preferred Term (or System Organ Class) using the worst severity grade.

Separate summaries will be prepared for TEAEs classified as severe or life-threatening (\geq Grade 3); study treatment-related AEs; AEs leading to treatment interruption, modification, or discontinuation; SAEs; and death.

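### Scheduled CMV testing after screening exists only in the idelalisib arm, so the CMV and infection rows of the TEAE summaries carry a detection difference against the comparator

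*Combined protocol and SAP*

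**What the plan says.** Tables 1 and 2 both schedule CMV IgG plus an antigen or PCR test for every patient at screening. From then on the arms differ. Section 7.4.5 defines CMV monitoring as "CMV antigen or PCR test for patients with positive CMV serology or history of CMV infection who are receiving treatment with idelalisib". Table 2 carries the matching row, with tests on Day 1 of Cycles 1 to 7, on Day 1 of Cycle 8 and beyond, and at end of treatment (EOT). Table 1 has no such row. For either arm, Section 7.4.5 adds: "Additional sample(s) may be collected and analyzed if clinically indicated".

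In Table 5 a positive PCR or antigen test is a sufficient trigger, and the action is: "Withhold idelalisib until the infection and viremia have resolved". Section 6.8.5 repeats the hold. Table 4, for loncastuximab tesirine, has no CMV rule.

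Under Section 8.1.3, laboratory abnormalities that "lead to pharmaceutical product interruption, modification, or discontinuation must be recorded as an AE". Section 9.8.1 summarizes all TEAEs and, separately, "AEs leading to treatment interruption, modification, or discontinuation". It does not distinguish events found by scheduled monitoring from events found because a patient was ill. Section 9.8 states that safety is descriptive.

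**The concern.** The same asymptomatic viremia is treated differently by arm. In a CMV-positive idelalisib patient it is looked for every four weeks, leads to a hold, and becomes an AE. In a CMV-positive loncastuximab tesirine patient it will usually go unseen. Targeted monitoring on idelalisib is a safety measure and is not in question; the side-by-side reading of the resulting rates is.

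The sample size was set to give safety data on about 100 loncastuximab tesirine patients, and the idelalisib arm is the natural reference for them. That arm has about 50 patients, so each extra patient with an event moves a row by 1/50 = 2 percentage points. A few monitoring-detected cases could make the comparator's infection profile look worse for reasons of ascertainment alone. Section 8.1.3 also asks for the diagnosis in place of the laboratory result where one fits, so the AE term may not show later how the event was found.

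**Working it through.** The documents give no CMV incidence, seroprevalence or interruption rate, so there is no stated figure to reproduce. The check has three parts.

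**1. Side-by-side ascertainment for a CMV-positive patient**

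| Step | Idelalisib | Loncastuximab tesirine |
|---|---|---|
| Screening CMV test | Yes (Table 2) | Yes (Table 1) |
| Scheduled test on treatment | Day 1 of each 4-week cycle, plus EOT | None |
| Unscheduled test | If clinically indicated (7.4.5) | If clinically indicated (7.4.5) |
| Hold on a positive test alone | Yes (Table 5, 6.8.5) | No rule (Table 4) |
| AE recording forced by a hold | Yes (8.1.3) | Not by this route |
| Separate handling in 9.8.1 | None | None |

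Scheduled Day 1 tests for an eligible idelalisib patient who stays on treatment:
- Through week 24: 24/4 + 1 = 7, of which 6 fall after the first dosing day.
- Through week 52: 52/4 + 1 = 14, of which 13 fall after the first dosing day.
- Loncastuximab tesirine: 0 in both periods.

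**2. Illustration of size, with equal true viremia in both arms**

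All three inputs are assumptions from outside the documents:
- p, the share of patients who are CMV-positive: 40–80%
- v, viremia on treatment among them: 5–20%
- s, the share of viremia found without surveillance: 0–50%

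Formulas: idelalisib detected = p × v; loncastuximab tesirine detected = p × v × s; artefactual gap = p × v × (1 − s).

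- Smallest gap: 0.40 × 0.05 × (1 − 0.50) = 1 point (2.0% v 1.0%).
- Middle case: 0.60 × 0.10 = 6.0% (3 of 50) v 6.0% × 0.25 = 1.5% (1.5 of 100), a gap of 4.5 points.
- Largest gap: 0.80 × 0.20 × (1 − 0) = 16 points (16%, or 8 of 50, v 0%).

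Across the grid idelalisib shows 2–16% and loncastuximab tesirine 0–8%. The gap is positive whenever s is below 1. The direction of the detection effect therefore follows from the design, while the size follows only from the assumptions.

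**3. Does this carry over to the whole interruption table?**

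Other arm-specific hold rules act in the opposite direction. Table 4 holds loncastuximab tesirine for Grade 3 or higher neutropenia or thrombocytopenia, whereas Table 5 maintains idelalisib at Grade 3. Table 4 holds for Grade 2 or higher edema or effusion, and Table 5 has no Grade 2 rule for these. Section 1.2.3 reports Grade 3 or higher neutropenia in 16.9% and thrombocytopenia in 12.0% of patients in the Phase 1 study of loncastuximab tesirine, so these rules may matter. With no CMV rate to set against them, the net direction cannot be derived.

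**The case against.** Several stronger readings are tempting, and the documents do not support them.

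- A reader might infer that the table of AEs leading to interruption is inflated for idelalisib by construction. The opposing hold rules in Tables 4 and 5 mean that this is not shown.
- A reader might infer that every positive test forces an interruption. The EOT test cannot, because treatment has already stopped. EOT is also preferably at least 30 days after the last dose, so a finding there may fall outside the TEAE window. Viremia present before the first dose that does not worsen is not treatment-emergent.
- A reader might infer that viremia on loncastuximab tesirine can never be recorded. Section 7.4.5 allows clinically indicated samples in either arm, and Section 8.2 elicits symptoms at each visit. Only the scheduled route is closed.
- A reader might take the whole idelalisib arm to be monitored. Monitoring is confined to patients with positive CMV tests or a CMV history.

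The broader defence is that nothing formal depends on this. Safety is descriptive, the safety objective concerns loncastuximab tesirine, and the pausing rules in Section 4.3 use Grade 5 toxicity, Grade 4 skin toxicity and Grade 4 edema or effusion. Section 9.8.1 does not specify a by-arm layout, Section 9 leaves detail to the SAP, and CMV events can be found by Preferred Term. All of this stands and limits the point to interpretation. It does not remove the point: a Preferred Term identifies CMV but not how it was detected, and that is most reliably captured prospectively.

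The defence is also right that a hold under Table 5 is a real interruption. Stripping only the CMV holds from the interruption table, while keeping the holds specific to Table 4, would introduce a tilt of its own.

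**Conclusion.** The point holds for the CMV and infection rows of the TEAE summaries. Those rows carry a detection difference against the comparator, because only idelalisib patients who are CMV-positive or have a CMV history are tested on a schedule and a positive test on treatment becomes an AE. The 1 to 16 point range is illustrative only. It assumes equal true viremia in both arms and rests on inputs that the documents do not contain. Part of any observed excess may be a real effect of idelalisib, which is a reason to show the data both ways and not to exclude events. The net direction for the interruption table is not established. No hypothesis test or pausing rule is affected. This is a cheap improvement to how the safety data are read, and it leaves the design as it is.

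**What to change.** Change the analysis text only (Section 9.8.1 and the SAP), with no change to testing or clinical rules:

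1. Flag each CMV event as monitoring-detected or clinically prompted.
2. Report viremia or antigenemia found only by scheduled monitoring as a separate row.
3. Show the infection summary with and without that row.
4. Base any between-arm statement about CMV on symptomatic or clinically prompted cases, which either arm can generate.
5. Leave the table of AEs leading to interruption intact, and footnote it to say that hold rules and CMV surveillance differ by arm.

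The cost is one eCRF or programming flag, one extra version of the infection table and a footnote.
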